4.3 Justification for Dose

Not Applicable.

4.4 End of Study Definition

A participant is considered to have completed the study if she has completed all phases of the study including the last visit shown in the Schedule of Activities (SoA), Section 1.3.

5. Study Population

5.1 Inclusion Criteria

In order to be eligible to participate in this study, an individual must meet all of the following criteria:

1. Female, between the age of 18 and 80
2. OD symptoms as indicated by an affirmative response to either questions 7, 8 or 14 of the Pelvic Floor Distress Inventory (PFDI):
 - a. Do you feel you need to strain too hard to have a bowel movement?
 - b. Do you feel you have not completely emptied your bowels at the end of a bowel movement?
 - c. Does part of your bowel ever pass through the rectum and bulge outside during or after a bowel movement?
3. Rectal hypermobility defined as a compression ratio greater than 50% according to ultrasound
4. Patient planning on undergoing surgery for the repair of pelvic organ prolapse within the next 12 months
5. Patient who is not pregnant and does not intend to become pregnant in the next 2 years
6. Available for 24-months of follow-up
7. Stated willingness to comply with all study procedures and availability for the duration of the study
8. Able to complete study assessments, per clinician judgment
9. Able and willing to provide independent written informed consent

10. Stable cardiovascular and respiratory status to meet candidacy in vaginal or laparoscopic surgeries

5.2 Exclusion Criteria

An individual who meets any of the following criteria will be excluded from participation in this study:

1. Contraindication to abdominal (history of severe intrabdominal surgery) and transvaginal rectopexy in the opinion of the treating surgeon
2. History of previous surgery that included any type of surgery for rectal prolapse
3. Pelvic pain or dyspareunia due to levator ani spasm that would preclude a PMT program
4. Previous adverse reaction to synthetic mesh
5. Current cytotoxic chemotherapy or current or history of pelvic radiation therapy within 12 months
6. History of two inpatient hospitalizations for medical comorbidities in the previous 12 months

5.3 Lifestyle Considerations

Not Applicable.

5.4 Screen Failure

Screen failures are defined as participants who consent to participate in the clinical trial but are not subsequently randomly assigned to the study intervention or entered in the study. A minimal set of screen failure information is required to ensure transparent reporting of screen failure participants, to meet the Consolidated Standards of Reporting Trials (CONSORT) publishing requirements and to respond to queries from regulatory authorities. Minimal information includes demography, screen failure details, eligibility criteria, and any serious adverse event (SAE).

Individuals who do not meet the criteria for participation in this trial (screen failure) may not be rescreened.

5.5 Strategies for Recruitment and Retention

Recruitment and informed consent will occur in two participating medical centers: 1) NorthShore University HealthSystem, and 2) Weill Cornell Medical Center- New York Presbyterian. Participants will be recruited from principal investigator and colleague's patient population. Female, between the age of 18 and 80, with and without vaginal prolapse who report obstructed defecation symptoms in more than 50% of their bowel movements with significant rectal hypermobility will be contacted directly during outpatient clinic visit to learn more about the study.

In addition, an electronic medical records messaging system will be utilized for recruitment. A list of eligible patients will be identified using the inclusion criteria and ICD-10 codes. Once eligible patients are identified, permission will be obtained from the patients' clinicians to include them in the messaging outreach. With the clinicians' permission, the research team will send electronic medical record messages with study information.

Because this study requires long-term participation, contact information for the participant will be collected during the consent process. Prior to each visit, participants will receive reminder calls regarding the upcoming visit.

Compensation

Participants will receive compensation for participating in the study. For the completion of MR defecography, the participant will be compensated \$100. For the completion of the surgery, the participant will be compensated \$100. For

each of the post-operation visits completed (2 weeks, 2-12-24 months), the participant will be compensated \$50. In total, the participant can be compensated up to \$400.

Participants will be responsible for all costs that would normally incur as part of routine care, including costs related to the surgical treatment. There will be no charge associated with follow-up visits and post-operative ultrasounds.

6. Study Intervention

6.1 Study Intervention(s) Administration

6.1.1 Study Intervention Description

Transvaginal Sacrospinous Rectopexy Surgical Technique

The posterior vaginal wall dissection is started with a horizontal incision in the mid-posterior vaginal wall. Dissection is carried down to the sacrospinous ligament (SSL) bluntly on each side. Sacrospinous ligament sutures are placed using a push-and catch suturing device (Capio Slim, Boston Scientific Corporation, USA) to deliver a single 0-polydioxane suture (Monodek, Teleflex Medical OEM) into each ligament approximately 2-2.5 cm medial to the ipsilateral ischial spine (Figure 5). With one finger inside the rectum, the suture is passed through the lateral rectal ligament and rectal muscularis layer, as a two-bite running suture, at a point 7-8 cm cephalad to the anal verge. After tying down the knot on the first side, rectal suture placement is then performed on the contralateral side; this sequential suturing and tying down of left and right sided rectal suspensions allows for assessment and fine-tuning of the rectal suspension and avoidance of excess tension or stretching of the rectal wall. After suspension of the rectum bilaterally, three additional interrupted 0 polydioxane sutures are used to reattach the midline posterior vaginal wall to the midline anterior rectal wall at the same level (7-8 cm cephalad from the anal verge); these sutures provide reinforcement and tension relief to the midline rectum between each lateral SSL suspension suture and serve to close a potential enterocele space.

[figure not shown]

Figure 5: This computational 3D model is created based on MRI images of a normal nulligravid healthy volunteer. The suturing sites on rectum and sacrospinous ligament used for transvaginal sacrospinous rectopexy and related landmarks are demonstrated here in coronal (A) and sagittal (B) views

Laparoscopic Abdominal Ventral Rectopexy Surgical Technique

The surgery is performed under general anesthesia with patient in steep Trendelenburg position. Usually 4 ports are created. Supra-umbilical port is used as camera port. The rectosigmoid junction is identified and retracted to the left. A "J shaped" peritoneal incision is given extending from the sacral promontory to the anterior peritoneal reflection distally. Right hypogastric nerve and ureter are identified and safeguarded. With combined blunt and sharp dissection, a wide plane is developed in the Rectovaginal/rectovesical space. Any posterior rectal mobilization or lateral dissection is avoided at this stage. A strip of Prolene mesh (Ethicon Endosurgery, Blue Ash, Ohio, United States), trimmed to 3 cm x 17 cm, is prepared and inserted into the pelvic cavity. One end of mesh is fixed to the anterior surface of the distal most part of the rectum using polypropylene sutures. Similarly, it is fixed to the lateral borders of the rectum. Care is taken to avoid full thickness bite into the rectal wall in order to prevent mesh contamination. Finally, the proximal end of mesh is fixed to the sacral promontory using same sutures. Proximal traction on the rectum is avoided while fixing the mesh. The peritoneum is then re-approximated to completely cover the mesh.

Conventional Vaginal Prolapse Surgery

To minimize the number of confounding variables and reduce the complexity of analysis, types of conventional vaginal prolapse surgery will be limited to the following:

1. Vaginal prolapse repair surgery –
 - a. Anterior vaginal repair surgery
 - b. Posterior vaginal repair surgery
 - c. Vault suspension
2. Abdominal prolapse repair surgery –
 - a. Sacrocolpopexy
3. Tension-Free Vaginal Tape

6.1.2 Dosing and Administration

Not applicable.

6.2 Preparation/ Handling/ Storage/ Accountability

6.2.1 Acquisition and Accountability

At both study sites, all investigators will perform the dynamic pelvic ultrasound. MR defecography will be performed by trained personnel at each site. Transvaginal sacrospinous rectopexy will be performed by urogynecologists. Laparoscopic abdominal ventral rectopexy will be performed by colorectal surgeons.

Per Objective Structured Assessment of Technical Skill (OSATS), competency criteria for the novel transvaginal sacrospinous rectopexy will be performing three to five cases under the supervision of [name] [name] and/or [name] until achieving the following milestone:

1. The surgeon was able to perform all aspects of the procedure safely and competently.

A second or third year urogynecology fellow or a second-year colorectal fellow will be able to assist in the surgeries under the direct supervision of investigators.

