2.3 Risk/Benefit Assessment

2.3.1 Known Potential Risks

Pelvic Exam

There is no immediate or long-range risk from a speculum exam and a quantified assessment of prolapse. The exam may create mild transient discomfort.

Written Questionnaires & Verbal Interviews

Answering these questions may make some participants temporarily uncomfortable. While not specifically addressed in the instructions, participants may elect not to answer some personal questions. All acquired information will be kept confidential by identifying the forms with study numbers only, keeping the results and the list linking names to study numbers in a password-protected database. Access to file cabinets containing paper copies will only be granted to the PI and study coordinators.

Dynamic Pelvic Ultrasound

Ultrasounds are minimally invasive, part of routine urogynecology care, and conducted by trained medical personnel. The exam may cause transient, mild discomfort, but pose little to no immediate or long-range risk.

MR Defecography

The defecography may cause discomfort due to imaging in a closed environment, participants can stop the imaging anytime during the test if they feel uncomfortable. Patients at risk for injury from MR scans are those with pacemakers, aneurysm clips, or shrapnel fragments. There is a minimal risk of skin burns from the radiofrequency (RF) coil. The defecography poses little to no long-range risk.

Surgical Procedures

For the surgical procedure, standard risks of surgery apply including bleeding, infection, and injury to nearby organs including the bowel, bladder, and ureters. There is a potential risk of pain following the surgical procedure. There is potential mesh related risks including mesh erosion, pain, infection, and fistulas.

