 - a. The first measurement will be the straight distance between the posterior cul de sac and anorectal junction.
 - b. The second measurement will be the perpendicular distance between the cul de sac and the pubo-coccygeal line.
 - c. The third measurement will be the perpendicular distance between the anorectal junction and the pubo-coccygeal line.
10. The relative change in length of the straight distance between the posterior cul de sac and the anorectal junction (CDS to ARJ) as observed on MR defecography will be used to define a compression ratio, which will

again be calculated as a percentage using the following formula: $\text{Compression ratio} = 100 * (\text{CDS to ARJ length at rest} - \text{CDS to ARJ septum length at evacuate}) / \text{CDS to ARJ length at rest.}$

PROD Trial
Research Standard Operating Procedure

SOP TITLE: Dynamic Pelvic Ultrasound	Version # 1
SOP NUMBER: PROD_SOP_2	Page 42 of 50

PURPOSE:

To describe expectations for completing Dynamic Pelvic Ultrasound for the PROD Trial.

PERSONNEL RESPONSIBLE:

Trained investigators of the PROD Trial.

PROCEDURES:

- The ultrasound procedure will be performed and read by trained investigators, including Drs. [name] and [name] at NorthShore University HealthSystem and Drs. [name] and [name] at Weill Cornell Medical Center- New York Presbyterian.
 - o The dynamic pelvic ultrasound image will be saved and re-evaluated in a blinded manner retrospectively to confirm the results of the initial reading.
- The competency criteria for the ultrasound procedure will be performing three to five cases under the supervision of [name] [name] and/or [name] until achieving the following milestone:
 - o The physician was able to perform all aspects of the procedure safely and competently.
- The principal investigator of the study, [name] [name], will review the data quality of the ultrasound procedures for the first ten ultrasounds completed.

Dynamic Pelvic Ultrasound:

1. Imaging will be obtained at the time of the study visit using:
 - a. BK Medical bk3000 with
 - b. 3D X14L4 (9038) Endocavity Transducer (frequency range: 14-4 MHz, focal range: 3-60 mm)
2. All ultrasound studies will be performed in the office setting with the patient in the dorsal lithotomy position, with hips flexed and abducted.
3. No preparation will be required, and no rectal or vaginal contrast will be used.

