4. Patients will be instructed to arrive to the office with a partially full bladder, and to avoid excessive pressure on surrounding structures that might distort the anatomy, the probe will be inserted into the vagina in a neutral position.
5. 360 degree endovaginal ultrasound volumes and dynamic ultrasound videos will be saved for further analysis.
6. For measurements, the distance between the posterior cul de sac and anorectal junction (“rectovaginal septum length”) will be measured both at rest and during Valsalva straining efforts using a dynamic imaging protocol in the mid-sagittal plane, allowing posterior compartment structures to be visualized. It should be noted that for Valsalva straining efforts, patients will be instructed to relax their pelvic floor while increasing intra-abdominal pressure. All images will include the cul de sac apically and the levator plate/anorectal junction caudally in order to standardize framing of the anatomy, and the dynamic recording will be started with the patient at rest and captured for 5 seconds of Valsalva straining (see Figure 1 top left & right).

a. “Compression ratio” will be calculated as a means to quantify the relative change in length of the rectovaginal septum (RVS), in other words the degree of hypermobility / sliding rectum, and is expressed as a percentage using the following formula: $CR = (RVS_r - RVS_v) / RVS_r * 100$ where RVS_r (Rectovaginal Septum) and RVS_v represent the RVS length at rest and Valsalva.

[figure not shown]

Figure 1: 2D dynamic endovaginal posterior compartment ultrasound of a patient with obstructed defecation symptoms at rest (left image) and at strain (right image). Rendering of an aluminum can is used to illustrate the concept of the rectal compression seen above. LP: Levator Plate, RVS: Rectovaginal Septum

PROD Trial
Research Standard Operating Procedure

SOP TITLE: Surgical Procedures	Version # 1
SOP NUMBER: PROD_SOP_3	Page 44 of 50

PURPOSE:

To describe expectations for completing surgical procedures (Transvaginal Sacrospinous Rectopexy and Laparoscopic Abdominal Ventral Rectopexy) for the PROD Trial.

PERSONNEL RESPONSIBLE:

Investigators performing surgical procedures of the PROD Trial.

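### No rule stops a surgeon from acquiring the primary-endpoint ultrasound of her or his own patient, and the blinded re-read cannot correct how the strain was coached

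*Combined protocol and SAP*

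**What the plan says.** On who scans, section 6.2.1 states: "At both study sites, all investigators will perform the dynamic pelvic ultrasound". Appendix B (the ultrasound SOP) states: "The ultrasound procedure will be performed and read by trained investigators". It then names two people per site, introduced by a word that makes them examples and not a closed list.

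On who operates, section 6.2.1 states "Transvaginal sacrospinous rectopexy will be performed by urogynecologists" and "Laparoscopic abdominal ventral rectopexy will be performed by colorectal surgeons". Appendix C assigns the operations to "Investigators performing surgical procedures of the PROD Trial". Surgeons are therefore within the group that section 6.2.1 allows to scan.

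On the measurement, the ratio compares septum length at rest with its length during Valsalva (section 3). Appendix B says that "patients will be instructed to relax their pelvic floor while increasing intra-abdominal pressure", and the strain is "captured for 5 seconds of Valsalva straining". Patient position and image framing are also fixed. No effort target, pressure reading or number of attempts is given.

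On masking, section 6.3 says that surgeons, participants and other research personnel cannot practicably be masked. It tries to keep the coordinator blinded for questionnaires only. For the ultrasound, the one masking step is a retrospective blinded re-evaluation of the saved image to confirm the first reading (section 6.3 and Appendix B).

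A participant is a failure if the ratio exceeds 20% (sections 3 and 8.1), and the primary analysis uses the 24-month value (section 9.4.2).

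**The concern.** A weaker strain shortens the septum less and so lowers the ratio. The examiner gives the instruction, knows the allocation and may have done the operation. Without any intent, an examiner who hopes for a good result may encourage less vigorous straining or stop sooner.

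Blinded re-reading protects against biased measurement of a recording. It does not protect against differences in what was elicited before the recording existed.

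The trial has one primary endpoint, dichotomised at a fixed cut-off, and its stated hypothesis is that the transvaginal operation is superior (section 9.1). If one arm were more often scanned by its own surgeons, a modest difference in coaching could appear as a difference in success rate. This cannot be repaired once the scans have been made.

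**Working it through.** **1. Is own-surgeon scanning allowed?** Section 6.2.1 allows every investigator to scan. Appendix C makes the surgeons investigators. No section, SOP or schedule requires that the follow-up scanner be someone other than the surgeon. It is therefore allowed in both arms.

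**2. Do the existing safeguards reach acquisition?**

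| Safeguard | What it controls | Coaching effort by an unmasked operator? |
|---|---|---|
| Three to five supervised ultrasound cases (Appendix B) | Skill | No |
| Principal investigator review of the first ten ultrasounds (Appendix B) | Early data quality | No |
| Fixed position, framing, start at rest, 5 seconds of strain (Appendix B) | Duration and view | In part: time is fixed, force is not |
| Blinded re-read of the saved recording (section 6.3, Appendix B) | Measurement on the recording | No |

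**3. Could exposure differ by arm?** Section 2.3.1 says: "Ultrasounds are minimally invasive, part of routine urogynecology care, and conducted by trained medical personnel". Urogynecologists perform the transvaginal operation and colorectal surgeons the laparoscopic one, so it is plausible that more transvaginal patients would be scanned by their own surgeon. This is an inference; the specialties of the named sonographers cannot be seen.

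**4. How large could the effect be?** The plan gives no figure to reproduce here, and nothing in it says how far the ratio moves with effort or operator. The following is an illustration.

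Inputs:
- Cut-off 20% (section 3).
- SD 14.4, from the transvaginal case series at 12 months (section 4.2).
- Planned success of 70% and 93%, so failure of 30% and 7% (section 9.2).
- Assumptions: a normal distribution, and a measured ratio lowered by d = 3 or 5 points in one arm.

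Formula: if the failure rate without a shift is f, and z is the normal deviate with upper-tail area f, the shifted failure rate is P(Z > z + d/14.4). Here 3/14.4 = 0.208 and 5/14.4 = 0.347.

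| Failure without shift | z | d = 3 | d = 5 | Fall in failure |
|---|---|---|---|---|
| 30% | 0.524 | P(Z > 0.733) = 23.2% | P(Z > 0.872) = 19.2% | 6.8 to 10.8 points |
| 7% | 1.476 | P(Z > 1.684) = 4.6% | P(Z > 1.823) = 3.4% | 2.4 to 3.6 points |

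**5. Effect on the test.** Suppose true success is 70% in both arms, with 48 evaluable per arm (section 9.2), and one arm's ratio is shifted by d = 5.
- SD 14.4: apparent success = P(Z < 0.524 + 0.347) = 80.8%.
- SD 18.4 (the preoperative SD in section 4.2): 5/18.4 = 0.272, and P(Z < 0.796) = 78.7%.

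A two-sided 5% pooled z-test, ignoring clustering, would then be significant in about 23% and 16% of trials respectively, instead of 5%. This assumes that the whole arm is shifted. If only some patients in the arm are affected, the figures are smaller.

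**The case against.** **Direction.** A reader might infer that the design favours the transvaginal operation because its surgeons scan their own patients while laparoscopic patients are scanned by someone uninvolved. The documents do not establish this. Section 6.2.1 read literally also covers colorectal investigators. Names are removed. Laparoscopic patients may have concomitant prolapse surgery (sections 4.1 and 6.1.1), and the plan does not say who performs it, so a urogynecologist may have operated on them too. The direction is conditional.

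**The operator list.** A reader might take Appendix B to restrict scanning to two people per site, in conflict with section 6.2.1. It does not, because the named people are examples. The two places differ in precision; they do not contradict each other.

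**Size.** The case series mean of 19.6% at 12 months lies almost on the cut-off. Using it as the baseline, failure falls from 48.9% to 40.7% or 35.4% for shifts of 3 or 5 points, which is 8 to 14 points. That is not a fair headline, since it implies 49% failure where the plan assumes 7% or 30%. The shifts themselves are assumed throughout.

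**Safeguards.** Training, early review, fixed framing and saved dynamic video are real protections, and the re-reader sees the recorded strain. No section describes choosing among clips. This narrows the gap to straining effort at acquisition.

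**Remedy.** Recording three strains and taking the largest ratio would raise measured ratios in both arms against an unchanged 20% cut-off. If applied only after surgery, it would also break comparability with baseline. That remedy should not be used.

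What remains is that own-surgeon scanning is allowed and that no safeguard controls unmasked coaching.

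**Conclusion.** The point stands as a correctable design weakness, not as a demonstrated bias. The documents establish three things: surgeons may acquire the primary-endpoint scan of their own patients, the measurement depends on a coached effort that is not measured, and blinding begins only after the recording is made.

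Bias in the treatment comparison needs a further condition that cannot be checked from the documents: own-surgeon scanning must be more common in one arm and must affect the strain obtained. Under the assumed 3 to 5 point shifts, the distortion is about 7 to 11 points from a 30% failure rate and about 2 to 4 points from a 7% rate, against a planned difference of 23 points. That would not by itself create the planned effect, but at the higher failure rate it could materially raise the chance of a false-positive result. The change is worth making because it is cheap now and impossible after follow-up.

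**What to change.** Amend section 6.2.1 and Appendix B as follows.

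1. Each post-operative study ultrasound is acquired by a trained investigator who neither performed nor assisted at that participant's surgery. Any exception is recorded as a protocol deviation.
2. The same fixed Valsalva instruction script is used at baseline and at every follow-up scan.
3. The operator's ID is recorded for each scan, and a sensitivity analysis of the primary endpoint excludes own-surgeon scans.
4. The statement in section 6.2.1 on who scans is made consistent with the Appendix B operator list.

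The way the ratio is calculated and the 20% cut-off stay unchanged.

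Cost: wording changes, one extra data field and less flexibility in scheduling. At least two scanning investigators are already named per site, so new staff should rarely be needed. If all of them took part in one operation, another trained operator would be required or a deviation recorded. Limits: the acquirer is still not masked, may be a close colleague of the surgeon, and a script standardises the instruction without measuring effort.
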